11 SOURCE DOCUMENTS AND ACCESS TO SOURCE DATA/DOCUMENTS

Each participating site will maintain appropriate medical and research records for this trial, in compliance with ICH E6, Section 4.9 and regulatory and institutional requirements for the protection of confidentiality of subjects. As part of participating in this study, each site will permit authorized representatives of the sponsor(s), MSG, and regulatory agencies to examine (and when required by applicable law, to copy) clinical records for the purposes of quality assurance reviews, audits, and evaluation of the study safety and progress.

Source data are all information, original records of clinical findings, observations, or other activities in a clinical trial necessary for the reconstruction and evaluation of the trial. Examples of these original documents and data records include, but are not limited to, hospital records, clinical and office charts, laboratory notes, memoranda, subjects' memory aid or evaluation checklists, pharmacy dispensing records, recorded data from automated instruments, copies or transcriptions certified after verification as being accurate and complete, microfiches, photographic negatives, microfilm or magnetic media, x-rays, and subject files and records kept at the pharmacy, at the laboratories, and medico-technical departments involved in the clinical trial. It is acceptable to use CRFs as source documents. If this is the case, it should be stated what data will be collected on CRFs and what data will be collected from other sources. ECRFs must be completed in their entirety regardless of the site's use of alternate source documents.

Refer to: (http://www.fda.gov/downloads/Drugs/Guidance/ucm073122.pdf).

12 QUALITY CONTROL AND QUALITY ASSURANCE

This section will address the plans for local quality assurance and quality control. (http://www.fda.gov/downloads/Drugs/Guidance/ucm073122.pdf).

All sites conducting research are required to have a plan in place for assuring the quality of the research being conducted.

Each site should have standard operating procedures (SOPs) for quality management which describe:

- How data will be evaluated for compliance with the protocol and for accuracy in relation to source documents.
- The documents to be reviewed (e.g., informed consents, eCRFs, clinic notes, product accountability), who is responsible, and the frequency for reviews should be identified, either in a formal quality management plan or in site SOPs.
- Methods of training for staff should be specified.

Additional information about site quality control are found in the Manual of Procedures

13 ETHICS/PROTECTION OF HUMAN SUBJECTS

13.1 Ethical Standard

The investigator will ensure that this study is conducted in full conformity with the principles set forth in The Belmont Report: Ethical Principles and Guidelines for the Protection of Human Subjects of Research of the US National Commission for the Protection of Human Subjects of Biomedical and Behavioral Research (April 18, 1979) and codified in 45 CFR Part 46 and/or the ICH E6; 62 Federal Regulations 25691 (1997).

If the study is conducted at international sites, compliance with the Declaration of Helsinki, CIOMS, and International Ethical Guidelines for Biomedical Research Involving Human Subjects (2002), or another country's ethical policy statement, whichever provides the most protection to human subjects.

13.2 Institutional Review Board

Each participating institution must provide for the review and approval of this protocol and the associated informed consent documents and recruitment material by an appropriate independent ethics committee (IEC) or IRB. Any amendments to the protocol or consent materials must also be approved before they are placed into use.

13.3 Informed Consent Process

Informed consent is a process that is initiated prior to the individual's agreeing to participate in the study and continuing throughout the individual's study participation. Extensive discussion of risks and possible benefits of this therapy will be provided to the subjects and their families. Consent forms describing in detail the study interventions/products, study procedures, and risks are given to the subject and written documentation of informed consent is required prior to starting intervention/administering study product. Consent forms will be IRB-approved and the subject will be asked to read and review the document. Upon reviewing the document, the investigator will explain the research study to the subject and answer any questions that may arise. The subjects will sign the informed consent document prior to any procedures being done specifically for the study. The subjects should have the opportunity to discuss the study with their surrogates or think about it prior to agreeing to participate. The subjects may withdraw consent at any time throughout the course of the trial. A copy of the informed consent document will be given to the subjects for their records. The rights and welfare of the subjects will be protected by emphasizing to them that the quality of their medical care will not be adversely affected if they decline to participate in this study.

A model informed consent form for subject participation is provided in the Manual of Procedures. Each institution should place the informed consent document in its own template. Each institution may add but not remove anything from the model consent form.

13.4 Exclusion of Women, Minorities, and Children (Special Populations)

Study participants will consist of males or females, age 18 or greater, who meet eligibility requirements. Women who are pregnant will be excluded from participation because of potential side effects of the study drugs on the fetus. There are no exclusion criteria based on race or ethnicity.

13.5 Subject Confidentiality

Subject confidentiality is strictly held in trust by the participating investigators, their staff, and the sponsor(s) and their agents. This confidentiality is extended to cover testing of biological samples and genetic tests in addition to the clinical information relating to participating subjects.

The study protocol, documentation, data, and all other information generated will be held in strict confidence. No information concerning the study or the data will be released to any unauthorized third party without prior written approval of the sponsor.

The study monitor or other authorized representatives of the sponsor may inspect all documents and records required to be maintained by the investigator, including but not limited to, medical records (office, clinic, or hospital) and pharmacy records for the subjects in this study. The clinical study site will permit access to such records.

14 DATA HANDLING AND RECORD KEEPING

14.1 Data Management Responsibilities

The investigator is responsible to ensure the accuracy, completeness, legibility, and timeliness of the data reported. All source documents should be completed in a neat, legible manner to ensure accurate interpretation of data. Black ink is required to ensure clarity of reproduced copies. When making changes or corrections, cross out the original entry with a single line, and initial and date the change. DO NOT ERASE, OVERWRITE, OR USE CORRECTION FLUID OR TAPE ON THE ORIGINAL.

Data reported in the eCRF derived from source documents should be consistent with the source documents or the discrepancies should be explained.

The MSG Coordinating Center and/or its designee will provide guidance to investigators on making corrections to the source documents and eCRF.

All source documents and laboratory reports must be reviewed by the clinical team and data entry staff at the site, who will ensure that they are accurate and complete. Adverse events must be graded, assessed for severity and causality, and reviewed by the site PI or designee.

Data collection is the responsibility of the clinical trial staff at the site under the supervision of the site PI. During the study, the investigator must maintain complete and accurate documentation for the study.

The MSGERC Statistical and Data Coordinating Center for this study will be responsible for data management, quality review, analysis, and reporting of the study data under the direction of the study statistician.

14.2 Data Capture Methods

Clinical data (including AEs, concomitant medications, and clinical assessments) and clinical laboratory data will be entered into a 21 CFR Part 11-compliant Internet Data Entry System (IDES) provided by The MSG Statistical and Data Coordinating Center. The data system includes password protection and internal quality checks, such as automatic range checks, to identify data that appear inconsistent, incomplete, or inaccurate. Clinical data will be entered directly from the source documents.

14.3 Study Records Retention

Study documents should be retained for a minimum of 2 years after the last approval of a marketing application in an ICH region and until there are no pending or contemplated marketing applications in an ICH region or at least 2 years have elapsed since the formal discontinuation of clinical development of the investigational product. These documents should be retained for a longer period, however, if required by local regulations. No records will be destroyed without the written consent of the sponsor, if applicable. It is the responsibility of the sponsor to inform the investigator when these documents no longer need to be retained.

14.4 Protocol Deviations

A protocol deviation is any noncompliance with the clinical trial protocol, Good Clinical Practice (GCP), or Manual of Procedure's requirements. The noncompliance may be either on the part of the subject, the investigator, or the study site staff. As a result of deviations, corrective actions are to be developed by the site and implemented promptly.

These practices are consistent with ICH E6:

- Compliance with Protocol, sections 4.5.1, 4.5.2, and 4.5.3
- Quality Assurance and Quality Control, section 5.1.1
- Noncompliance, sections 5.20.1, and 5.20.2.

It is the responsibility of the site to use continuous vigilance to identify and report deviations within 5 working days of identification of the protocol deviation, or within 5 working days of the scheduled protocol-required activity. All deviations must be promptly reported to the MSG Coordinating Center by Email or fax.

All deviations from the protocol must be addressed in study subject source documents. A completed copy of the MSG Protocol Deviation Form must be maintained in the regulatory file, as well as in the subject's source document. Protocol deviations must be sent to the local IRB/IEC per their guidelines. The site PI/study staff is responsible for knowing and adhering to their IRB/IEC requirements.

15 PUBLICATION POLICY

Following completion of the study, the investigator is expected to publish the results of this research in a scientific journal. The International Committee of Medical Journal Editors (ICMJE) member journals have adopted a trials-registration policy as a condition for publication. This policy requires that all clinical trials be registered in a public trials registry such as ClinicalTrials.gov*, which is sponsored by the National Library of Medicine. Other biomedical journals are considering adopting similar policies. **The MSG Coordinating Center will register this study in ClinicalTrials.gov.** Any clinical trial starting enrollment after 01 July 2005 must be registered on or before patient enrollment. For trials that began enrollment prior to this date, the ICMJE member journals will require registration by 13 September 2005, before considering the results of the trial for publication.

The ICMJE defines a clinical trial as any research project that prospectively assigns human subjects to intervention or comparison groups to study the cause-and-effect relationship between a medical intervention and a health outcome. Studies designed for other purposes, such as to study pharmacokinetics or major toxicity (e.g., Phase I trials), would be exempt from this policy.

APPENDIX A: SCHEDULE OF EVENTS

| Activities | Day 1 ^g (Baseline) | Day 7 (1 wk) +/- 3 days | Day 14 (2 wks) +/- 3 days | Day 28 (4wks) +/- 7 days | Day 42 (6 wks) +/- 3 days | Day 84 (3 mos) +/- 7 days | Day 180 (6 mos) +/- 7 days |
|---|----------------------------------|----------------------------------|------------------------------------|-----------------------------------|------------------------------------|------------------------------------|-------------------------------------|
| Informed Consent | Х | | | | | | |
| Review of Inclusion/Exclusion Criteria | × | | | | | | |
| Randomization | X | | | | | | |
| Medical History | X | | | | | | |
| Clinical Assessment: vital signs, PE ^a , & radiographs ^b ; | × | Х | Х | Х | Х | Х | × |
| Participant Administered SF-12 Quality of Life Survey | Х | | | | Х | | х |
| Tolerability | Х | | | Х | Х | | Х |
| βHCG - pregnancy test ^c | Х | | | | | | |
| Mycologic Assessment: clinical, urine and serum quantitative antigen levels^d & serum antibodies ^{e,f} | х | | х | Х | Х | Х | х |
| Serum and Urine for future use: blood, urine, saliva, sputume | X | | Х | X | Х | Х | Х |
| Plasma PK ^f | | Χ | Х | | Х | | |
| Chemistry: Creatinine, AST and Alkaline Phosphatase, Total Bilirubin ^f | Х | | Х | Х | Х | Х | х |
| Hematology: CBC with Differential ^f | X | | | X | | X | X |
| HIV Status: Documentation of any positive test; Documentation of Negative test 30 days or less prior to start of study drug. | Х | | | | | | |
| Antifungal Therapy (Pre- and during study) | Х | Х | Х | Х | Х | Х | Х |
| Dose Modifications | | | Х | X | Х | Х | |
| Study Drug Dosing & Accountability | Х | Х | Х | Х | Х | Х | Х |
| Concomitant Therapy | Х | Х | Х | Х | Х | Х | Х |
| Adverse Events | Х | Х | Х | Х | Х | Х | Х |
| Days of Hospitalization, ICU | Х | Х | Х | Х | Х | Х | Х |

^a Complete physical exam on baseline; targeted physical exams for all other visits.

b Radiograph results that were performed as standard of care to diagnose or assess the fungal infection.

^C Urine or Serum pregnancy test is acceptable.

^d Histoplasma and Coccidioides urine and serum quantitative antigen.

^e Collection of sputum, if associated with the IFI and available.

^fChemistry and hematology will be processed at the site for safety evaluations; PK samples will be sent to a central lab for processing; see Manual of Procedures for specimen handling procedures;

gBaseline Visit: Study drug is be started on Day 1. Visit windows for Day 7, 14 and 42 will be a +/-3 day window. All other visits have a +/- 7 day window.

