States, Canada and Central/South America (Approximately: 40 Histoplasmosis, 20 Coccidioidomycosis, 20 other endemic mycoses)

Number of Sites: Approximately 20 total sites in US, Canada, and Central/South

America

Study Duration: This study is estimated to be opened for 18 months after initiation (12

month patient accrual, 6 month treatment period).

Subject Each participant will be enrolled in the study for 180 days

Participation

Objectives:

The objectives of this study are to compare PK, tolerance, safety, and efficacy of SUBA-Itraconazole study drug versus conventional itraconazole in a randomized open-label trial followed by a second stage of continuing open-label study drug.

Stage I - Randomized, Open-Label, Parallel Group

Primary Objective

- PK at Day 14
- Tolerability at Day 42

Secondary Objective

- PK at Day 7
- PK at Day 42
- Efficacy by Day 42
- Safety by Day 42
- QOL (including hospital/ICU visits) Assessments by Day 42

Stage II - Open-Label Extension

Primary Objective

- Efficacy by Day 180
- Tolerability by Day 180

Secondary Objective

- Safety by 180
- QOL (including hospital/ICU visits) Assessments by Day 180

Description of Study Design:

[figure not shown]
This is a prospective, multi-center, randomized, open-label parallel arm study involving patients with proven or probable invasive endemic fungal infection to ascertain the pharmacokinetics, safety, efficacy, tolerability and health economics of oral SUBA-itraconazole compared to conventional itraconazole. Patients will receive randomized open-label study drug (SUBA-itraconazole or conventional itraconazole) over a 42 day period and then continue therapy until Day 180 or earlier if Principal Investigator determines discontinuation of therapy is safe. Patients will be stratified based on clinically reported infection with the human immunodeficiency virus (HIV).

The study sample size will be 80 evaluable patients – target enrollment (three groups: approximately 40 histoplasmosis, 20 coccidioidomycosis, 20 other endemic fungal infections).

Estimated Time to Complete Enrollment

12 Months

Schematic of Study Design:

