5.2 Subject Exclusion Criteria

All subjects meeting any of these listed exclusion criteria at baseline will be excluded from study participation:

- 1. Significant liver dysfunction as evidenced by at least 5 times greater than upper limits of normal baseline ALT, AST, alkaline phosphatase, or total bilirubin.
- 2. Use of an alternative antifungal therapy (IV or oral) for more than 14 days for this infection with the exception of Coccidioidomycosis. Subjects with Coccidioidomycosis who previously received fluconazole therapy for more than 14 days may be included, if in the opinion of the investigator, they are having an inadequate response or, are intolerant of fluconazole (e.g. due to adverse events). Such subjects must washout from fluconazole for 7 days (~5 half-lives of fluconazole) before starting investigational therapy.
- 3. Evidence of CNS infection.
- 4. Unable to take PO medications.
- 5. Female subjects who are lactating or pregnant.

- 6. Female subjects should be:
 - a) Postmenopausal for 1 year,
 - b) Post-hysterectomy or bilateral oophorectomy,
 - c) If of child bearing potential have a negative β-HCG at screening and using highly effective method of birth control throughout course of study or remain abstinent for duration of study.
- 7. Male subjects with female partner(s) of child-bearing potential, must agree to use a medically acceptable method of contraception during the study. If their partner is pregnant, males must agree to use a condom; if their partner is of child-bearing potential, their partner must additionally be using one of the following methods: hormonal contraception, intra-uterine device, diaphragm, or cervical cap. Spermicides alone are not an acceptable method of contraception. No sperm donations for 90 days post last dose of study therapy.
- 8. Documented intolerance, allergy or hypersensitivity to an azole.
- 9. Inability to comply with study treatment, study visits, and study procedures.
- 10. Known history of congestive cardiac failure on medical treatment, fungal endocarditis, or other causes of ventricular dysfunction that may outweigh the benefit of itraconazole.
- 11. Patients with active TB
- 12. Concurrent use of astemizole, rifampin/rifampicin, rifabutin, ergot alkaloids, long acting barbiturates, carbamazepine, pimozide, quinidine, neostigmine, terfenadine, ketoconazole, valproic acid, or St. John's wort in the 5 days prior to first administration of study drug.

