6.2 Dosage, Preparation and Administration of Study Intervention/Investigational Product

Study participants will be randomized to receive either open-label SUBA-Itraconazole or conventional itraconazole. Each treatment arm will be dosed as follows:

Arm A: Open-Label SUBA-itraconazole 65 mg Capsules – administered with food

Stage 1

- Day 1 3: two 65 mg capsules, three times daily
- Day 4 42: two 65 mg capsules, twice daily

Stage 2:

Day 43 – 180: two 65 mg capsules, twice daily.

Arm B: Conventional Itraconazole 100 mg Capsules – administered with food Stage 1:

- Day 1 3: two 100 mg capsules, three times daily
- Day 4 42: two 100 mg capsules, twice daily

Stage 2:

Day 43 – 180: two 100 mg capsules, twice daily).

Based on standard of care for invasive endemic fungal infection, some participants will be prescribed conventional itraconazole (non-study drug) after Day 180 for up to a year or beyond, as prescribed by their physician. Information for discounted itraconazole will be provided at the end of the study to help defray costs.

[figure not shown]

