7.2 Enrollment/Baseline

Patients consenting to the study will be further evaluated for inclusion and exclusion criteria, medical history, physical examination, pregnancy test (blood or urine BHCG), mycologic assessment, antigen and antibody levels, radiography (if clinically indicated); serum chemistry, serum hematology. See Appendix A for study procedures per visit.

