8.2 Laboratory Evaluations

Safety laboratory evaluations (Hematology, Biochemistry and Urine Pregnancy Tests) will be conducted by the local site laboratory as part of standard of care for treating patients with endemic mycoses.

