8.2.1 Clinical Laboratory Evaluations

- 8.2.1.1 Hematology: hemoglobin, hematocrit, white blood cells (WBC) with differential count, platelet count.
- 8.2.1.2 Biochemistry: creatinine, total bilirubin, alanine aminotransferase (ALT), aspartate aminotransferase (AST).
- 8.2.1.3 Blood or Urine Pregnancy test, to be done within 24 hours prior to study intervention and results must be available prior to administration of study product.
- 8.2.1.4 HIV: HIV Testing must be performed and resulted no more than 30 days prior to start of study unless previous positive findings are documented in source documents.

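### No pregnancy test is scheduled after baseline, although pregnant women are excluded for fetal risk and dosing can run to Day 180

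*Combined protocol and SAP*

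**What the plan says.** Section 13.4 keeps pregnant women out of the trial "because of potential side effects of the study drugs on the fetus", and exclusion 5 in Section 5.2 applies this at entry. The baseline test is well specified. Section 7.2 lists it among the enrolment evaluations, and Section 8.2.1.3 says it is "to be done within 24 hours prior to study intervention and results must be available prior to administration of study product". The Appendix A row "βHCG - pregnancy test" agrees: it is marked under Day 1 and blank at Days 7, 14, 28, 42, 84 and 180.

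Dosing goes on long after that test. For Days 43 to 180, Section 6.2 gives Arm A "two 65 mg capsules, twice daily" and Arm B the same capsule count and frequency at 100 mg. The Protocol Summary allows a shorter course: patients "continue therapy until Day 180 or earlier if Principal Investigator determines discontinuation of therapy is safe".

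Two provisions bear on the later period. Exclusion 6c requires a woman of child-bearing potential to be "using highly effective method of birth control throughout course of study or remain abstinent for duration of study". Section 8.2 states: "Safety laboratory evaluations (Hematology, Biochemistry and Urine Pregnancy Tests) will be conducted by the local site laboratory as part of standard of care". It gives no time for any test after baseline.

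**The concern.** The reason for excluding pregnant women does not end at the first dose. If fetal exposure justifies keeping them out, it also justifies checking, while women are being dosed, that participants have not become pregnant. A site that follows Appendix A exactly would test once and not again. If contraception fails, detection depends on symptoms, on a clinical assessment that happens to reveal the pregnancy, or on local practice. Until then the woman keeps taking a drug that she could not have started had she been pregnant at baseline.

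What is at stake is participant and fetal safety. The primary outcomes and their analysis are not affected.

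**Working it through.** The plan gives no figure of its own on this point, so there is none to reproduce. The check is a count and some interval arithmetic.

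**Inputs.** Visit days 1, 7, 14, 28, 42, 84 and 180, with their windows (Section 7.3, Appendix A). Pregnancy test marked at Day 1 only (Appendix A). Dosing to Day 180 (Section 6.2). 80 participants randomised (Section 10.2).

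**Current schedule.**
- Visits after baseline: 6. Of these, with a scheduled pregnancy test: 0.
- Interval without a scheduled test, for a patient dosed throughout: 180 − 1 = 179 days.
- With the last visit at the end of its +7 day window: 187 − 1 = 186 days.

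**Which later visits are worth using.** Appendix A already collects urine at Days 14, 28, 42, 84 and 180, and its footnote c accepts urine or serum. The documents do not say how soon after conception a test turns positive, so take a lag of L days as an assumption.
- With L = 14, a conception on Day 1 is detectable from Day 15, so a Day 14 test finds no on-study conception.
- With L = 7, a Day 14 test could find conceptions up to Day 7 (14 − 7), and the Day 28 test would find those as well.
- With L = 21, a Day 14 test again finds none.

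Day 14 therefore adds little, and Day 28 is a sensible first repeat.

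**Schedule with tests at Days 28, 42, 84 and 180.**
- Gaps: 28 − 1 = 27; 42 − 28 = 14; 84 − 42 = 42; 180 − 84 = 96. Their sum is 179.
- Longest gap as a share of the period: 96/179 = 53.6%.
- Longest possible gaps at the window limits: 35 − 1 = 34; 45 − 21 = 24; 91 − 39 = 52; 187 − 77 = 110.
- Conceptions too late for the Day 180 test to show: the last L days. With L = 14 these are conceptions after Day 166, or 14/179 = 7.8% of the period. With L = 7 the share is 7/179 = 3.9%; with L = 21 it is 21/179 = 11.7%.

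**Number of tests.** At most 4 × 80 = 320, if every participant were an eligible woman. If half were (assumption), 4 × 40 = 160.

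**Handling of an on-study pregnancy, by section.**
- Section 6.3 lets the investigator stop drug at discretion. Its list of toxicity triggers does not name pregnancy.
- Section 5.3.2 allows discontinuation for an adverse event or for violating an exclusion criterion. The wording is permissive, and Section 5.2 applies the criteria at baseline.
- Section 8.4.2 makes a birth defect a serious adverse event. Section 8.5.1 requires serious events to be reported within 24 hours of site awareness, and requires suspected drug-related ones to be reported even after the study ends.
- Section 8.4.1 says to report when in doubt. No section says whether an uncomplicated pregnancy counts as an adverse event.

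The means to stop drug and a route for the worst outcome are therefore present. An explicit rule for reporting and following an uncomplicated pregnancy is not.

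**The case against.** The best defence is that the risk is already controlled. A negative result is needed before the first dose, and highly effective contraception or abstinence is required throughout. Section 8.2 lists urine pregnancy tests among the local safety laboratory work. All six later visits include clinical and adverse-event assessments, and Section 7.5 allows unscheduled visits for safety issues. Sections 7.2 and 8.2.1.3 and Appendix A do not contradict one another, so this is a choice about how closely to monitor and not an error.

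Most of that stands. Contraception lowers the chance of pregnancy but does not reveal a failure. Section 8.2 says where tests are run, not when, and Sections 7.3 and 7.4 refer to Appendix A for timing. Later examinations are targeted (Appendix A, footnote a), visits may be by telemedicine (Section 7.3), and no scheduled visit falls between Days 84 and 180. Detection is possible, but no scheduled procedure ensures it.

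A reader might go further and infer that the plan has no way to deal with an on-study pregnancy. The documents do not support that. Sections 6.3 and 5.3.2 permit stopping, and Sections 8.4.2 and 8.5.1 capture a birth defect as a serious event. The Manual of Procedures, which holds the serious-event form and the model consent, and the Investigator Brochure and package insert are separate documents that may contain a pregnancy rule.

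**Conclusion.** The point holds as a gap in scheduled safety monitoring: up to 179 days of dosing (186 with the visit window) with no scheduled pregnancy test, in women who would have been excluded if pregnant at entry. The figure assumes dosing to Day 180; an earlier stop shortens it.

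It is tempting to read 179 days as the length of undetected fetal exposure. It is not. It is only the interval without a scheduled test, during which contraception is required and six visits offer a chance of clinical detection. The documents give neither the number of women of child-bearing potential nor a pregnancy rate, so no expected number of pregnancies can be stated.

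The absence of an explicit reporting rule is secondary and depends on what the Manual of Procedures says. The change is worth making because it is cheap and protects participants. It has no bearing on the validity of the results.

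**What to change.** - **Appendix A, pregnancy-test row.** For women of child-bearing potential still on study drug, add a urine or serum test at Days 28, 42, 84 and 180, or at end of therapy if earlier. When a visit is held by telemedicine, use the remote blood draw that Section 7.3 allows.
- **Section 8.5.1.** Add one sentence, for example: *A pregnancy in a participant is reported to the MSG Coordinating Center within 24 hours of site awareness, prompts immediate review of whether to stop study drug, and is followed to outcome.* If the Manual of Procedures already contains such a rule, a cross-reference is enough.

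The cost is one changed table row, one sentence, and at most four inexpensive tests per eligible woman at visits where urine is already collected. Rarely, a pregnancy will need follow-up contact after Day 180. The change does not close the 96-day interval between Days 84 and 180 or find conceptions shortly before the last test. An extra test between those visits would be a new procedure outside the visit schedule, and the documents give no basis for choosing its day, so none is proposed.
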